5.5.11 Withdrawal of consent

Patients may voluntarily withdraw consent and cease to participate in the study for any reason at any time.

Withdrawal of consent occurs only when (1) a subject does not want to participate in the study anymore and (2) does not want to participate in any further visits or assessments and (3) does not want any further study related contacts and (4) does not allow analysis of already obtained biologic material.

If a patient withdraws consent, the investigator must make every effort to determine the primary reason for this decision and record this information in the eCRF. No further assessments must be conducted. All biological material that has not been analyzed at the time of withdrawal must not be used and must be destroyed. Further attempts to contact the patient are not allowed unless safety findings require communicating or follow-up.

NOTE: The investigator must also notify Novartis of the premature withdrawal.

5.5.12 Lost to follow-up

For patients whose status is unclear because they fail to appear for study visits without stating an intention to discontinue, the investigator should show "due diligence" by documenting in the source documents steps taken to contact the subject, e.g., dates of telephone calls, registered letters, etc. A patient should not be considered lost to follow-up until his/her scheduled end of study visit would have occurred.

Patients who are discontinued from the study for any reasons will not be replaced.

5.5.13 Emergency breaking of assigned treatment

Emergency un-blinding should only be undertaken when it is essential to treat the patient safely and efficaciously. Most often, study treatment discontinuation and knowledge of the possible treatment assignments are sufficient to treat a study patient who presents with an emergency condition.

For patients enrolled prior to protocol amendment #1

Emergency code breaks are performed using the IRT system. When the investigator contacts the system to un-blind a patient, he/she must provide the requested patient identifying information and confirm the necessity to un-blind the patient. The investigator will then receive details of the drug treatment for the specified patient and a fax or email confirming this information. The system will automatically inform the Novartis monitor for the site and the Global Trial Leader that the code has been broken.

The un-blinded treatment code should not be recorded on the eCRF.

It is the investigator's responsibility to ensure that there is a procedure in place to allow access to the IRT in case of emergency. If appropriate, the investigator will inform the patient how to contact his/her backup in cases of emergency when he/she is unavailable. The investigator will provide protocol number, study drug name, patient number, and instructions for contacting the local Novartis CPO (or any entity to which it has delegated responsibility for emergency code breaks) to the patient in case emergency un-blinding is required at a time when the investigator and backup are unavailable.

Study drug must be discontinued after emergency un-blinding. Study drug must also be discontinued for any patient whose treatment code has been inadvertently broken or for any non-emergency reason (see [Section 5.5.10](#)).

For patients enrolled after protocol amendment #1, in case an emergency un-blinding of the core study treatment code is required, the investigator will have to follow the procedure described in the core study protocol CBYM338E2202.

5.5.14 Study completion and post-study treatment

The study will complete when the last patient completes his/her Study Completion visit, and any repeat assessments associated with this visit have been documented and followed-up appropriately by the Investigator.

The investigator must provide follow-up medical care for all patients who are prematurely withdrawn from the study, or must refer them for appropriate ongoing care.

5.5.15 Early study termination

The study can be terminated at any time for any reason by Novartis. Should this be necessary, the subject should be seen as soon as possible and treated as a prematurely discontinued subject. The investigator may be informed of additional procedures to be followed in order to ensure that adequate consideration is given to the protection of the subject's interests. The investigator will be responsible for informing IRBs/IECs of the early termination of the trial.

6 Visit schedule and assessments

For patients enrolled after the protocol amendment #1, the full assessment schedule is presented in [Table 6-1](#) below. Patients enrolled prior to the protocol amendment #1 will be followed according to the visit scheduled presented in [Table 6-2](#).

In order to allow sufficient reflection time for the informed consent process, the extension study may be presented and discussed early enough in the core study in order to allow the ICF signature process to be done at the Week 25/core EOT visit. The ICF must not be signed before the core EOT visit to avoid complications in the safety reporting requirements.

Patients following [Table 6-1](#) should be seen for all visits on the designated day within a recommended 'visit window' of +/- 14 days. Day 1 must be the same day as the EOT visit of the core (i.e. the visit date is the date of the EOT visit of the core).

Patients should arrive to the visit fasted when blood samples for laboratory assessments will be taken at that visit.

Assessments for a particular visit may be split over several days. These may not be consecutive days but should respect the visit window period.

Below are some recommendations for organizing and performing the study assessments at visits with blood sampling.

- Assessments should be performed sequentially in the morning as follows: ECG collection, vital signs, blood sampling.
- After blood sampling, patients should be offered breakfast.

For patients enrolled prior to the protocol amendment #1, the visits window to be applied is +/- 3 days. When scheduling the assessments of a visit, the same principle as stated above should apply. In addition, study treatment administration should be the last procedure.

[figure not shown]
Patients who discontinue the study should **NOT** be considered withdrawn from the study UNLESS they withdraw their consent (see [Section 5.5.11](#)). They should return and complete the EOS visit. If they fail to return for these visits for unknown reasons, every effort should be made to contact them as specified in [Section 5.5.12](#).

Patients enrolled prior to the protocol amendment #1, who prematurely discontinue study treatment, should return as close to 28 days following the last dose received and complete the EOT visit. Their EOS visit should be scheduled 4 weeks after their EOT.

At a minimum, patients will be contacted for reporting and follow-up of serious adverse events during the 30 days following the last study visit, including a final contact at the 30-day point. Documentation of attempts to contact the patient should be recorded in the source documentation.

Table 6-1 Assessment schedule for patients enrolled after the protocol amendment #1

Epoch	Screening epoch	Post-treatment follow-up epoch						
Timepoint	1	1	2	3	4	5	6	7
Site Visit	1(EOT)	1 (EOT)			2			3 (EOS) ⁵
Phone contact			X	X		X	X	
Month	7	7	8	9	10	11	12	13
Week	25	25	29	33	37	41	45	49
Day	1	1	29	57	85	113	141	169
Obtain Informed consent	x							
Inclusion/Exclusion criteria	x							
Relevant medical history		x ²						
Demography	x							
Physical examination		*			s			s
Body weight		*1			x			x
Body height		*1						
Blood pressure/pulse rate (sitting)		*1			x			x
Electrocardiogram		*1			x			x
Laboratory samples (hematology, biochemistry, vitamin D)		*			x			x
Vitamin D3 supplementation		Equivalent to daily administration of 800 IU to 4000 IU						
Supervised exercise		*1			x			
Home based exercise		2-3 times per week						
6 minute walk test		*1			x			x
Short physical performance		*1			x			x

[figure not shown]

Epoch	Screening epoch	Post-treatment follow-up epoch						
battery								
Exercise diary		Daily by the patient to report level of home based exercise						
DXA		*						x
Diet assessment/ nutritional status		*1			x			x
AE ³ /SAE ⁴		x ²	Any time as per AE/SAE reporting requirement					
Concomitant therapies		x ²	Any time as per Concomitant therapies reporting requirement					
Comments	Any time as per investigator judgement							
Epoch disposition	x							x

S : mark procedure documented in the patient's source file only and not in the CRF
 
* Assessment performed at EOT visit of the core study. 3rd party data will be automatically transferred.
 
¹ Site must re-enter the data from EOT of core study onto the corresponding eCRF page of the extension study
 
² Ongoing events/conditions (i.e. SAEs/AEs, concomitant medications, cardiovascular and other relevant medical history) at EOT of the core study must be recorded on the appropriate eCRF of the extension study
 
³ From the time of signing informed consent until EOS
 
⁴ From the time of signing informed consent until 30 days after a patient stopped study participation
 
⁵ Patients who discontinue study should return for EOS visit within the next 4 weeks unless they withdraw their consent
								

Table 6-2 Assessment schedule for patients enrolled prior to the protocol amendment #1

Epoch	Screening Epoch	Treatment Epoch												Post-treatment Follow-up Epoch
		1	2	3	4	5	6	7 (EOT) ⁴	8(EOS) ⁴					
Visit	1	1	2	3	4	5	6	7 (EOT) ⁴	8(EOS) ⁴					
Month	7	7	8	9	10	11	12	13	14					
Week	25	25	29	33	37	41	45	49	53					
Day	1	1	29	57	85	113	141	169	197					
Hours	Pre-dose	Pre-dose/ *EOT of core	0	Pre-dose	0	Pre-dose	0	Pre-dose	0	Pre-dose	0	Pre-dose	0	
Obtain informed consent	x													
Inclusion / Exclusion criteria	x													
Relevant med. hist. / Current med. cond./Cardiovascular medical his.		X ⁷												
Concomitant Meds / Therapies		X ⁷	Any time as per concomitant therapies reporting requirement											
Demography	X ⁸													
Physical examination ⁹		*8		s				s				s		s
Body weight		*8		x				x				x		x
Body height		*8												x
Blood pressure / Pulse rate (sitting)		*8		x				x				x		x ⁴
Electrocardiogram (ECG)		*8		x				x				x		x

Epoch	Screening Epoch	Treatment Epoch												Post-treatment Follow-up Epoch
		1	2	3	4	5	6	7 (EOT) ⁴	8(EOS) ⁴					
Visit	1	1	2	3	4	5	6	7 (EOT) ⁴	8(EOS) ⁴					
Month	7	7	8	9	10	11	12	13	14					
Week	25	25	29	33	37	41	45	49	53					
Day	1	1	29	57	85	113	141	169	197					
Hours	Pre-dose	Pre-dose/ *EOT of core	0	Pre-dose	0	Pre-dose	0	Pre-dose	0	Pre-dose	0	Pre-dose	0	
Echocardiography		*												x ¹⁰
Hematology		*		x				x						x
Clinical Chemistry		*		x				x						x
Cardiac Panel		*												
Vitamin D quantification		*						x						x
Vitamin D3 supplementation			Equivalent to daily administration of 800 IU to 4000 IU											
Supervised exercise		*8				x				x				x ⁴
Home-based exercise			2-3 times per week											
6 minute walk test		*8				x				x				x
Short physical performance battery		*8				x				x				x
Exercise diary			Daily by the patient to report level of home based exercise											
Lean Body Mass and Appendicular skeletal mass index by DXA		*						x						x ⁴
Randomization		x												

Epoch	Screening Epoch	Treatment Epoch												Post-treatment Follow-up Epoch		
		1	2	3	4	5	6	7 (EOT) ⁴	1	2	3	4	5		6	7 (EOT) ⁴
Visit	1	1	2	3	4	5	6	7 (EOT) ⁴	1	2	3	4	5	6	7 (EOT) ⁴	8(EOS) ⁴
Month	7	7	8	9	10	11	12	13	7	8	9	10	11	12	13	14
Week	25	25	29	33	37	41	45	49	25	29	33	37	41	45	49	53
Day	1	1	29	57	85	113	141	169	1	29	57	85	113	141	169	197
Hours	Pre-dose	Pre-dose/ *EOT of core	0	Pre-dose	0	Pre-dose	0	Pre-dose	0	Pre-dose	0	Pre-dose	0			
Drug administration			x		x		x		x		x		x			
Diet assessment / nutritional status		x			x				x					x ⁴		
AEs ^{2,7}		As required per AE reporting requirement														
SAEs ^{3,7}		As required per SAE reporting requirement														
Comments		Any time as per investigator judgement														
Epoch disposition ⁶	x														x ⁴	x ⁴

* Assessment performed at EOT visit of the core study. 3rd party data will be automatically transferred.

S : mark evaluation documented in the patient source file only and not in the CRF

² For randomized patients, from the time of signing informed consent until EOS

³ For all patients, from the time of signing informed consent until 30 days after a patient stopped study participation

- 4 Patients who discontinue study treatment should return for EOT visit 28 days after last dose received and continue into the Post-Treatment Epoch with EOS visit 4 weeks after EOT unless they withdraw their consent
- 5 Screening epoch to obtain informed consent, demography and confirm I/E criteria for extension study is captured at visit 1 prior to dosing.
- 6 Disposition captured at completion of each epoch: Screening; Treatment; and Post-Treatment Follow-up
- 7 Ongoing SAEs/AEs at EOT of core must be recorded as AEs/SAEs on the appropriate eCRF of the extension study. Ongoing concomitant medications and ongoing cardiovascular/relevant medical history/current medical conditions must be recorded on the appropriate eCRF pages of the extension study.
- 8 Site must re-enter the data from EOT of core onto the corresponding eCRF page of the extension study.
- 9 Physical examinations are performed at scheduled visits. Details of the exams are recorded in the source documents. Medical history of the core study which is ongoing at EOT of core is included in the Relevant and Medical History eCRF of the extension study. Significant findings observed after informed consent signature of the extension study which meet the definition of an Adverse Event must be appropriately recorded on the Adverse Event eCRF of the extension study
10. Echocardiography at EOT will only be performed for patients with new abnormal finding on the echocardiography reading of the core Week 25/EOT visit.

.

6.1 Patient demographics/other characteristics at study entry

6.1.1 Subject demographics

Subject demographic data to be collected on all patients include: date and /or year of birth, sex, race, predominant ethnicity. The demographic data of the extension study will be the same as the demographic data of the core study. Instructions for completing the extension study eCRF will be provided in the eCRF completion guidelines (eCCGs).

6.1.2 Other characteristics at study entry

At the core study week 25 EOT visit before a patient enters the extension study, the investigator must review the following baseline data of the core study (CBYM338E2202): Cardiovascular History eCRF, Medical History eCRF. Any cardiovascular or medical history that is still ongoing at week 25 EOT of the core study must be recorded on the Cardiovascular History eCRF or Medical History eCRF of the extension study.

Similarly, any concomitant medications ongoing at week 25 EOT of the core study must be recorded on the Prior and Concomitant Medications eCRF of the extension study.

In addition, any ongoing AEs at week 25 EOT of the core study must be recorded as AEs in the extension study eCRF.

Instructions for completing the extension study eCRF will be provided in the eCCGs.

6.2 Treatment exposure and compliance

Throughout the study, patients will be required to participate in an exercise program with defined minimum requirements (see [Section 3.1](#)). Patients will record their training sessions on an exercise diary to track program adherence. The content of the paper diary will be recorded in the Exercise diary eCRF.

In addition patients will have vitamin D supplementation (see [Section 5.1.2](#)) recorded in the prior and concomitant eCRF.

For patients enrolled prior to the protocol amendment #1 only:

Patients will receive all study medication at the Investigator site. Study medication will be administered by site personnel, compliance will be ensured by appropriate training of site personnel. The date and time of administration of study drug will be recorded in the dosage administration record section of the eCRF.

6.3 Efficacy

Physical function efficacy assessments will be done at all sites by trained site personnel to ensure standard results. Training of the assessment protocols will be provided to each study site team by Novartis.

Efficacy measurements in the study will include:

- 6MWT to assess physical function
- SPPB to assess physical function
- Usual Gait Speed to assess physical function
- Total LBM and ASMI assessed by DXA to measure lean body mass and skeletal muscle mass of the arms and legs, respectively.

6.3.1 6 minute walk test

The 6 minute walk test (6MWT) is a simple, economical and reproducible test that measures how many meters a person can walk in 6 minutes. Repeated measurement of the 6MWT over time has been used in studying numerous musculoskeletal, pulmonary, and cardiovascular conditions and is a validated outcome in investigational drug trials.

Patients will be instructed by the test administrator using a script and established testing protocol. The testing should be conducted on an individual basis (patient and testers) with no additional audience or support other than that of the trained personnel conducting the test. If a walking aid is required, patients will be asked to use the least assistive walking aid that in their opinion will enable them to complete the 6MWT test safely. Patients should be encouraged to use the same walking aid when performing all tests throughout the study. A change in walking aid to perform the test is permitted if required for safety reasons (e.g., deterioration of balance). The testing should occur at approximately the same time of the day throughout the study to prevent any possible diurnal variations. The same test administrator should perform all repeat tests on a patient whenever possible to reduce technician-related differences in test performance.

Complete details of course set-up, test administration, equipment and recording into the eCRF are described in the CBYM338E2202E1 Outcomes Manual.

6.3.3 Gait speed

Gait speed in this study will be assessed as part of the SPPB, over a 4 meter distance of a 6 meter course. This test assesses a person's usual walking speed, which is defined as the speed a person normally walks from one place to another (e.g., walking from one store to another).

Usual gait speed represents one of the most suitable physical performance measures to evaluate older persons. Gait speed is associated with physical activity levels, changes in strength of lower extremity muscles, frailty and falls ([Newman et al 2003](#), [Chandler et al 1998](#), [Cesari et al 2005](#)).

Gait speed is a well-established measure of physical function, it has shown to predict future disability in diverse community-dwelling elderly populations and is sensitive to changes in physical status in response to an intervention (e.g., physical activity and rehabilitation) ([Barthuly et al 2012](#)). Poor functional performance as measured by slow or declining gait speed is related to an increased risk of disability, hospitalization and mortality ([Studenski et al 2011](#)), whereas improvements in gait speed are related to reductions in mortality risk ([Hardy et al 2007](#)). For these reasons, gait speed has been suggested as a key indicator of overall health in the geriatric population.

[figure not shown]
Complete details of test administration, equipment and recording into the eCRF are described as part of the SPPB protocol listed in the CBYM338E2202E1 Outcomes Manual.

[figure not shown]
6.3.4 Total lean body mass and appendicular skeletal mass index (ASMI) assessed by DXA

Dual energy X-ray absorptiometry (DXA) will be used to assess changes in total LBM and ASMI. DXA instruments use an x-ray source that generates and is split into two energies to measure bone mineral mass and soft tissue from which fat and fat-free mass (or lean body mass) are estimated. The exam is quick (~5-6 min), precise (0.5-1%) and non-invasive. DXA scanners have the precision required to detect changes in muscle mass as small as 5%.

Studies have shown that quality assurance is an important issue in the use of DXA scans to determine body composition. DXA instrument manufacturer and model should remain consistent and their calibration should be monitored throughout the study. Use of a standardized scan acquisition protocol and appropriate and unchanging scan acquisition and analysis software is essential to achieve consistent results. Likewise, because of variability in interpretation of the scans, it is important to utilize centralized scan analysis by experienced staff.

Details of the test administration are provided in the CBYM338E2202E1 Imaging Manual.

6.4 Safety

6.4.1 Physical examination

A complete physical examination will include the examination of general appearance, skin (including special attention to telangectasias of the skin or nail-folds and acne), neck (including thyroid gland, and oral mucosa for evidence of bleeding, hypertrophy, ulceration, or other changes from baseline), eyes, ears, nose, throat, lungs, heart, abdomen, back, lymph nodes, extremities, vascular and neurological parameters. If indicated based on medical history and/or symptoms, rectal, external genitalia, breast, and/or pelvic exams may be performed.

Skin-related issues will be assessed by the investigator or assigned clinician at each physical exam time point. Particular attention should be devoted to the assessment of acne due to the previously noted increased incidence of acne in people treated with bimagrumab.

If possible, assessments for an individual patient should be performed by the same member of the study site staff throughout the study.

Information for all physical examinations must be included in the source documentation at the study site and will not be recorded on the eCRF. Medical history of the core study which is ongoing at EOT of core is included in the Relevant and Medical History eCRF of the extension study. Significant findings observed after informed consent signature of the extension study which

meet the definition of an Adverse Event must be appropriately recorded on the Adverse Event eCRF of the extension study.

6.4.2 Vital signs

Vital signs include blood pressure (BP) and pulse measurements. After the patient has been resting for 3 minutes in a seated position, systolic and diastolic BP will be measured using an automated validated device, with an appropriately sized cuff. In case the cuff sizes available are not large enough for the patient's arm circumference, a manual sphygmomanometer with an appropriately sized cuff may be used.

If vital signs are out-of-range, the Investigator may obtain two additional readings, so that a total of three consecutive assessments are made, with the subject seated quietly for approximately five minutes preceding each repeat assessment. All readings should be recorded on the eCRF.

Vital signs will be collected at scheduled visits indicated in [Table 6-1](#) and [Table 6-2](#) as appropriate. Whenever possible, at each visit, vital signs should be collected using the same arm.

6.4.3 Height and weight

Height in centimeters (cm) and body weight (to the nearest 0.1 kilogram [kg] in indoor clothing, but without shoes) will be measured at scheduled visits indicated in [Table 6-1](#) and [Table 6-2](#) as appropriate.

If a weight decrease of 5% or more compared to the core baseline is seen, a comprehensive diet assessment should be conducted as per [Section 5.1.2](#).

Body mass index (BMI) will be calculated using the following formula:

$$\bullet \text{ B M I } = \text{Body weight (kg)} / [\text{Height (m)}]^2$$

6.4.4 Laboratory evaluations

In the case where a laboratory result is outside the reference range for the laboratory parameter a decision regarding whether the result is of clinical significance or not shall be made by the Investigator and shall be based, in part, upon the nature and degree of the observed abnormality.

In all cases, the Investigator must document in the source documents, the clinical considerations (i.e., result was/was not clinically significant and/or medically relevant) in allowing or disallowing the subject to continue in the study.

Clinically relevant deviations of laboratory test results occurring during or at completion of the study should be evaluated for criteria defining an adverse event and reported as such if the criteria are met.

Repeated evaluations are mandatory until normalization of the result(s) or until the change is no longer clinically relevant. In case of doubt, Novartis personnel should be contacted.

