> 3 × ULN accompanied by symptoms ^b	
 Discontinue the study drug immediately Hospitalize if clinically appropriate Establish causality Complete liver CRF 	ALT, AST, TBL, Alb, PT/INR, ALP and γ GT until resolution ^c (frequency at investigator discretion)
> 3 to ≤ 5 × ULN (patient is asymptomatic)	
 Repeat LFT within the next week If elevation is confirmed, initiate close observation of the patient 	Investigator discretion Monitor LFT within 1 to 4 weeks
ALP (isolated)		
> 2 × ULN (in the absence of known bone pathology)	
 Repeat LFT within 48 hours If elevation persists, establish causality Complete liver CRF 	Investigator discretion Monitor LFT within 1 to 4 weeks or at next visit
TBL (isolated)		
> 2 × ULN (in the absence of known Gilbert)	
 Repeat LFT within 48 hours If elevation persists, discontinue 	ALT, AST, TBL, Alb, PT/INR, ALP and γ GT until resolution ^c (frequency at investigator discretion)

Criteria	Actions required	Follow-up monitoring
syndrome)	the study drug immediately 
 • Hospitalize if clinically appropriate • Establish causality • Complete liver CRF 	discretion) Test for hemolysis (e.g., reticulocytes, haptoglobin, unconjugated [indirect] bilirubin)
> 1.5 to ≤ 2 × ULN (patient is asymptomatic)	
 • Repeat LFT within the next week • If elevation is confirmed, initiate close observation of the patient 	Investigator discretion Monitor LFT within 1 to 4 weeks or at next visit
Jaundice	
 • Discontinue the study drug immediately • Hospitalize the patient • Establish causality • Complete liver CRF 	ALT, AST, TBL, Alb, PT/INR, ALP and γGT until resolution ^c (frequency at investigator discretion)
Any AE potentially indicative of a liver toxicity*	
 • Consider study drug interruption or discontinuation • Hospitalization if clinically appropriate • Establish causality • Complete liver CRF 	Investigator discretion

*These events cover the following: hepatic failure, fibrosis and cirrhosis, and other liver damage-related conditions; the non-infectious hepatitis; the benign, malignant and unspecified liver neoplasms

^aElevated ALT/AST > 3 × ULN and TBL > 2 × ULN but without notable increase in ALP to > 2 × ULN

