### Liver [REDACTED] enzyme abnormalities

Newly occurring or worsening liver enzyme abnormalities will be summarized, for each population separately, using:

- Number of subjects with newly occurring notable liver [REDACTED] enzyme abnormalities will be summarized similarly to those of vital signs. Notable criteria for the table:
  - ALT or AST > 3 x ULN
  - ALT or AST > 5 x ULN
  - ALT or AST > 8 x ULN
  - TBL > 1.5 x ULN
  - TBL > 3 x ULN
  - ALP > 2 x ULN
  - ALP > 5 x ULN
  - ALT or AST > 5 x ULN & TBL > 2 x ULN
  - ALP > 5 x ULN & TBL > 2 x ULN
  - Hy's law

- Shift tables of LFTs/[REDACTED] enzymes presenting a cross-tabulation of Week 25 and worst post Week 25 values
- Change from Week 25 summary tables of LFTs/[REDACTED] enzymes by visit.

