### Multiple assessments within visits

For visit multiple records may exist in one particular visit for a particular assessment (e.g. laboratory assessments). The following rules (unless otherwise specified) will be applied to obtain one value per patient per assessment per visit which will be used in the assessment by-visit summaries.

- the closest to the actual target visit day is chosen for both continuous variables and categorical variables based on continuous variables (if two assessments have the same distance, then the earlier one by assessment date or visit date will be chosen);
- For qualitative variables (i.e., laboratory abnormalities or most extreme values analysis), the worst/most extreme (high & low) record will be used.

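### Laboratory repeats prompted by abnormal results can replace early Week 37 and Week 49 values but never the Week 25 value, so by-visit summaries can modestly exaggerate recovery off drug

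*Protocol*

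**What the plan says.** **Which results are repeated.** Protocol 6.4.4 leaves the judgement on an out-of-range result to the site: "a decision regarding whether the result is of clinical significance or not shall be made by the Investigator". After describing clinically relevant deviations it adds: "Repeated evaluations are mandatory until normalization of the result(s) or until the change is no longer clinically relevant". It requires no repeat of a normal result. For liver tests, Protocol Appendix 1, Table 13-2 sets the timing: 48 hours for some elevations, and for the milder asymptomatic ones "Repeat LFT within the next week".

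**Which record is analysed.** The SAP 5.5.1 text on multiple assessments expects several records in one visit and gives laboratory data as its example. For by-visit summaries, "the closest to the actual target visit day is chosen for both continuous variables and categorical variables based on continuous variables". On ties, "if two assessments have the same distance, then the earlier one by assessment date or visit date will be chosen". A second bullet sends laboratory abnormalities and extreme-value analyses to the worst record. Neither bullet distinguishes a scheduled sample from a repeat.

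**Which outputs use it.** SAP 3.6.1.2 plans by-visit mean, SD, median, minimum and maximum for laboratory variables. For liver enzymes it also plans "Change from Week 25 summary tables of LFTs", by visit.

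**Where Week 25 sits.** Protocol Section 6 states: "Day 1 must be the same day as the EOT visit of the core". SAP 5.4 defines the Week 25 value as the Visit 1 assessment, and SAP 5.5.1 gives it target Day 1.

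**The concern.** The extra records are not a random sample of laboratory results. They exist because a result was abnormal, and they continue until it has settled. Choosing between the scheduled sample and a repeat by calendar distance lets some abnormal scheduled values drop out of the by-visit summaries in favour of later, usually better ones. Normal scheduled values have no required repeat to displace them.

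The selection also differs between the two ends of the comparison. Week 25 lies at zero distance from its target, so its value stays whatever it shows. Weeks 37 and 49 do not have that protection. A change-from-Week-25 table therefore compares an unselected value with a partly selected one, and the expected direction is apparent improvement. Safety after treatment withdrawal, judged partly on laboratory variables, is a secondary objective (Protocol 2.2), so these tables address a stated question.

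**Working it through.** **Inputs.** Visit windows of ±14 days (Population II) and ±3 days (Population I) come from Protocol Section 6. Analysis windows come from SAP 5.5.1. Repeat lags of 2 and 7 days come from Table 13-2; 14 days is an assumption. It is also assumed that repeats reach the analysis database, which no section excludes.

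**Reproducing the SAP windows.** Each boundary is the midpoint of adjacent targets, with the tie day given to the earlier visit. Week 37: (57 + 85)/2 = 71 and (85 + 113)/2 = 99, hence Days 72–99. Week 49: (141 + 169)/2 = 155 and (169 + 197)/2 = 183, hence Days 156–183. Both match. Relative to target the window is −13 to +14 days, which is 28 whole days. A Population II visit exactly 14 days early (Day 71 or 155) falls in the preceding window.

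**When a repeat wins.** Let d be the visit day minus the target day and r the lag to the repeat. The repeat is selected if |d + r| < |d|, that is, d < −r/2. At equality the earlier (scheduled) record is kept. A visit on or after the target day always keeps the scheduled value.

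**Share of such scheduled values replaced.**

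| Visit-day assumption | r = 2 | r = 7 | r = 14 |
|---|---|---|---|
| Visit must be early by at least | 2 days | 4 days | 8 days |
| Population II, uniform −13 to +14 | 12/28 = 43% | 10/28 = 36% | 6/28 = 21% |
| Population II, normal, SD 7 days | 41% | 31% | 14% |
| Population II, normal, SD 3 days | 31% | 12% | 1% |
| Population I, uniform −3 to +3 | 2/7 = 29% | 0% | 0% |
| Week 25, d = 0 | 0% | 0% | 0% |

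The normal rows use whole days. For example, with SD 3 and r = 7, P(d ≤ −4) = P(Z < −3.5/3) = 12%. The Week 25 row takes the sample as drawn on Day 1. Protocol Section 6 lets a visit be split over several days, but SAP 5.4 ties the Week 25 value to Visit 1 in any case.

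**Shift in a visit mean.** Shift = p × s × f, where p is the proportion of patients with a clinically relevant abnormal value, s the share replaced, and f the fall on repeat in SD units. The documents give neither p nor f. Assumed ranges are p = 1% to 10%, f = 1 to 4 SD, and s = 21.4% to 42.9% from the uniform row.

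- Low: 0.01 × 0.214 × 1 = 0.002 SD
- Middle: 0.05 × 0.357 × 2 = 0.036 SD
- High: 0.10 × 0.429 × 4 = 0.17 SD

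This treats every replacement as a fall of size f, so it is generous to the concern. Clustering of visits on target would lower s and the shift with it.

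**The case against.** The strongest reply is that nearest-to-target selection is pre-specified and comes with a worst-value safeguard. Liver shift tables use the worst value after Week 25. Notable liver thresholds are tabulated. All laboratory data are listed, with abnormal values flagged where normal ranges exist, and patients with any abnormal value have a separate listing. Clinically relevant deviations are also assessed as possible adverse events. A peak missing from a by-visit maximum is therefore not lost, and no formal hypothesis is tested. This stands, and it is why the point is minor. It does not cover the continuous by-visit summaries or the liver change tables, which the worst-record bullet does not reach.

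Four stronger readings are tempting but not supported:

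- *Abnormal values are generally swapped.* Replacement needs an early visit and a nearer repeat. It is a minority of cases in every scenario tried.
- *Replacement always runs towards normal.* Repeats continue until the result settles, so an early one may still be abnormal or worse. Table 13-2 provides for elevations that persist. The shares above count any replacement.
- *The reported percentage of abnormal patients falls.* No by-visit table of that percentage is clearly planned. Newly occurring notable values are handled as for vital signs, by epoch, and exclude values already notable at Week 25.
- *The bias is larger in active arms.* Protocol 3.6 reports ALT and AST rises with the drug but calls them transient. Population II's scheduled last dose is at core Week 21 (SAP 3.6.1.2), so Weeks 37 and 49 fall 16 and 28 weeks later. The same rule applies to placebo. The shift would scale with each arm's abnormality rate, but nothing shows that those rates differ at these visits.

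**Conclusion.** The point holds as a minor one. The asymmetry follows from rules that are written down: abnormality triggers repeats, calendar distance selects the record, and Week 25 is fixed at zero distance. Its expected direction is towards apparent recovery off drug.

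The 21% to 43% range for Population II depends on visits being spread evenly over the window. The protocol asks for visits on the designated day, so the clustered figures may be closer to practice. The shift in means rests wholly on assumed abnormality rates and falls on repeat, and is probably small. A reader might infer that the trial will give a false picture of laboratory recovery. The documents do not support that: the effect is confined to descriptive continuous summaries, and the worst-value outputs and listings show the signals.

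A related ambiguity also needs settling. A notable laboratory value is both a category derived from a continuous measurement (nearest record) and a laboratory abnormality (worst record). SAP 5.5.1 does not say which bullet governs.

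**What to change.** Add to SAP 5.5.1: *For laboratory by-visit summaries and change from Week 25, the sample collected at the scheduled visit is used; an unscheduled or repeat sample is used only if the scheduled one is missing or invalid. All records, including repeats, are used for notable-value, worst-value and shift tables.*

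Wherever a valid scheduled sample exists, this brings the replacement share at Weeks 37 and 49 to 0%, as at Week 25. It also settles which bullet governs notable values. The cost is this SAP text and a scheduled/repeat flag in programming. No new data are needed, and the protocol's repeat-testing rules are untouched.
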